12.3 Methods for Evaluation of Measurable Disease

All measurements should be taken and recorded in metric notation using a ruler or calipers. All baseline evaluations should be performed as closely as possible to the beginning of treatment and never more than 4 weeks before the beginning of the treatment.

The same method of assessment and the same technique should be used to characterize each identified and reported lesion at baseline and during follow-up. Imaging-based evaluation is preferred to evaluation by clinical examination unless the lesion(s) being followed cannot be imaged but are assessable by clinical exam.

Clinical lesions: Clinical lesions will only be considered measurable when they are superficial (e.g., skin nodules and palpable lymph nodes) and ≥10 mm diameter as assessed using calipers (e.g., skin nodules). In the case of skin lesions, documentation by color photography, including a ruler to estimate the size of the lesion, is recommended.

Chest x-ray: Lesions on chest x-ray are acceptable as measurable lesions when they are clearly defined and surrounded by aerated lung. However, CT is preferable.

Conventional CT and MRI: This guideline has defined measurability of lesions on CT scan based on the assumption that CT slice thickness is 5 mm or less. If CT scans have slice thickness greater than 5 mm, the minimum size for a measurable lesion should be twice the slice thickness. MRI is also acceptable in certain situations (e.g., for body scans), but NOT lung.

Use of MRI remains a complex issue. MRI has excellent contrast, spatial, and temporal resolution; however, there are many image acquisition variables involved in MRI, which greatly impact image quality, lesion conspicuity, and measurement. Furthermore, the availability of MRI is variable globally. As with CT, if an MRI is performed, the technical specifications of the scanning sequences used should be optimized for the evaluation of the type and site of disease. Furthermore, as with CT, the modality used at follow-up should be the same as was used at baseline and the lesions should be measured/assessed on the same pulse sequence. It is beyond the scope of the RECIST guidelines to prescribe specific MRI pulse sequence parameters for all scanners, body parts, and diseases. Ideally, the same type of scanner should be used and the image acquisition protocol should be followed as closely as possible to prior scans. Body scans should be performed with breath-hold scanning techniques, if possible.

PET-CT: At present, the low dose or attenuation correction CT portion of a combined PET-CT is not always of optimal diagnostic CT quality for use with RECIST measurements. PET-CT scans are not always done with oral and IV contrast. In addition, the PET portion of the CT introduces additional data which may bias an investigator if it is not routinely or serially performed. For these reasons, we will not allow PET-CT use for RECIST 1.1 response criteria.

Ultrasound: Ultrasound is not useful in assessment of lesion size and should not be used as a method of measurement. Ultrasound examinations cannot be reproduced in their entirety for independent review at a later date and, because they are operator dependent, it cannot be guaranteed that the same technique and measurements will be taken from one assessment to the next. If new lesions are identified by ultrasound in the course of the study, confirmation by CT or MRI is advised. If there is concern about radiation exposure at CT, MRI may be used instead of CT in selected instances.

Endoscopy, Laparoscopy: The utilization of these techniques for objective tumor evaluation is not advised. However, such techniques may be useful to confirm complete pathological response when biopsies are obtained or to determine relapse in trials where recurrence following complete response (CR) or surgical resection is an endpoint.

Cytology, Histology: These techniques can be used to differentiate between partial responses (PR) and complete responses (CR) in rare cases (e.g., residual lesions in tumor types, such as germ cell tumors, where known residual benign tumors can remain).

The cytological confirmation of the neoplastic origin of any effusion that appears or worsens during treatment when the measurable tumor has met criteria for response or stable disease is mandatory to differentiate between response or stable disease (an effusion may be a side effect of the treatment) and progressive disease.

12.4 Response Criteria

12.4.1 Evaluation of Target Lesions

Complete Response (CR): Disappearance of all target lesions. Any pathological lymph nodes (whether target or non-target) must have reduction in short axis to <10 mm.

Partial Response (PR): At least a 30% decrease in the sum of the diameters of target lesions, taking as reference the baseline sum diameters.

Progressive Disease (PD): At least a 20% increase in the sum of the diameters of target lesions, taking as reference the smallest sum on study (this includes the baseline sum if that is the smallest on study). In addition to the relative increase of 20%, the sum must also demonstrate an absolute increase of at least 5 mm. (Note: the appearance of one or more new lesions is also considered progressions).

Stable Disease (SD): Neither sufficient shrinkage to qualify for PR nor sufficient increase to qualify for PD, taking as reference the smallest sum diameters while on study.

12.4.2 Evaluation of Non-Target Lesions

Complete Response (CR): Disappearance of all non-target lesions and normalization of tumor marker level. All lymph nodes must be non-pathological in size (<10 mm short axis).

Non-CR/Non-PD: Persistence of one or more non-target lesion(s).

Progressive Disease (PD): Appearance of one or more new lesions and/or *unequivocal progression* of existing non-target lesions. *Unequivocal progression* should not normally trump target lesion status. It must be representative of overall disease status change, not a single lesion increase.

Although a clear progression of "non-target" lesions only is exceptional, the opinion of the treating physician should prevail in such circumstances, and the progression status should be confirmed at a later time by the review panel (or Principal Investigator).

12.4.3 Evaluation of Best Overall Response

The best overall response is the best response recorded from the start of the treatment until disease progression/recurrence (taking as reference for progressive disease the smallest measurements recorded since the treatment started). The patient's best response assignment will depend on the achievement of both measurement and confirmation criteria.

For Patients with Measurable Disease (i.e., Target Disease)

Target Lesions	Non-Target Lesions	New Lesions	Overall Response	Best Overall Response when Confirmation is Required*
CR	CR	No	CR	≥4 wks. Confirmation**
CR	Non-CR/Non- PD	No	PR	≥4 wks. Confirmation**
CR	Not evaluated	No	PR	
PR	Non-CR/Non- PD/not evaluated	No	PR	
SD	Non-CR/Non- PD/not evaluated	No	SD	Documented at least once ≥4 wks. from baseline**

PD	Any	Yes or No	PD	
Any	PD***	Yes or No	PD	no prior SD, PR or CR
Any	Any	Yes	PD	

^{*} See RECIST 1.1 manuscript for further details on what is evidence of a new lesion.

Note: Patients with a global deterioration of health status requiring discontinuation of treatment without objective evidence of disease progression at that time should be reported as "symptomatic deterioration." Every effort should be made to document the objective progression even after discontinuation of treatment.

For Patients with Non-Measurable Disease (i.e., Non-Target Disease)

Non-Target Lesions	New Lesions	Overall Response
CR	No	CR
Non-CR/non-PD	No	Non-CR/non-PD*
Not all evaluated	No	not evaluated
Unequivocal PD	Yes or No	PD
Any	Yes	PD

^{* &#}x27;Non-CR/non-PD' is preferred over 'stable disease' for non-target disease since SD is increasingly used as an endpoint for assessment of efficacy in some trials so to assign this category when no lesions can be measured is not advised

^{**} Only for non-randomized trials with response as primary endpoint.

^{***} In exceptional circumstances, unequivocal progression in non-target lesions may be accepted as disease progression.

13.0 CRITERIA FOR REMOVAL FROM STUDY

Study treatment will be discontinued for the following reasons:

- Progression of disease (unless patient agrees to continue treatment past progression)
- Persistent or unacceptable toxicity despite appropriate dose reductions
- · Withdrawal of consent
- If in the opinion of the investigator continuation on study poses unreasonable risks to the patient. This might include patients who fail to return for adequate follow-up, hampering the ability to monitor toxicities

Any patient discontinuing study drug should be seen at 30 days post discontinuation for the evaluations outlined in the study schedule. The patient's tumor status should be assessed clinically and, if appropriate, disease progression should be confirmed by radiological assessment.

After discontinuation of the study medication at any point in the study, all ongoing AEs or SAEs must be followed until resolution unless, in the investigator's opinion the condition is unlikely to resolve due to the patients underlying disease, or the patient is lost to follow up. All new AEs and SAEs occurring during the 30 calendar days after the last dose of study medication must be recorded, reported if applicable and followed to resolution as above. Patients should be contacted at least 30 days after discontinuing study medication to collect and /or complete AE information. Any untoward event occurring subsequent to the 30-day follow-up AE reporting period that the investigator assesses as possibly related to the study medication should also be reported as an AE.

Any patient, who has not yet shown objective disease progression, should continue to be followed as per RECIST 1.1.

The study and/or individual Cohorts may be discontinued if it is found that it is not feasible to reach the planned outcomes.

13.1 Treatment Past Progression:

If a patient is found to have progression of disease by RECIST 1.1 criteria, but in the opinion of the treating clinician is felt to potentially still derive benefit, after discussion with study PI, the patient may consent to continue with protocol directed treatment. If the patient decides to continue receiving treatment, the patient will be asked to sign a separate consent form. The treating clinicans discussion of treatment past progression with the patient should be documented in the medical record.

14.0 BIOSTATISTICS

This is a single institution, investigator initiated, open label, basket study exploring the efficacy of onapristone ER in PR+ recurrent or advanced gynecologic cancer that has been designed as three parallel Simon 2-Stage studies testing the recommended phase 2 dose of onapristone ER as a single agent or in combination with anastrozole in histologies of interest.

Three histologies of interest are being examined:

Cohort 1: Granulosa cell ovarian cancer (onapristone single agent)

Cohort 2: Low grade serous ovarian cancer (onapristone single agent)

Cohort 3: Endometrioid endometrial cancer (onapristone single agent)

Cohort 4: Granulosa cell ovarian cancer (onapristone in combination with anastrozole)

The null hypothesis for each basket is based on poor historical rates to systemic therapies in these histologies. While prospective data is lacking in patients with low grade serous ovarian cancer the retrospective response rate to chemotherapy is 4%, and 9% to available hormonal therapies [7, 8, 12, 13]. Granulosa cell, the most common type of sex-cord stromal ovarian cancer, generally has poor response rates to chemotherapy and is commonly treated with hormonal strategies, most commonly aromatase inhibitors, though the response rate to anastrozole in recurrent granulosa cell tumors is 2.5%. [9]. Endometrial cancer also has limited options with a 13% response rate to chemotherapy in the second line [10]. Megestrol acetate is the only systemic treatment FDA approved specifically for endometrial cancer and has shown response rates as high as 24% in conjunction with tamoxifen in the recurrent setting, but is not commonly used due to poor tolerance [11]. Tamoxifen as a single agent has a response rate of 10% in recurrent endometrial cancer[14, 15].

A short-coming of this design is that a basket study which implements multiple independent two-stage designs has a higher overall false-positive rate than a typical phase II study[16]. However, to modulate this effect we have limited this study to 4 baskets/cohorts. Sample size calculations are based on the Simon two-stage minimax design.

For Cohort 1 if \geq 1/14 complete or partial responses are seen by RECIST 1.1 criteria within 6 months of treatment (stage I) then the study will expand to stage II. If a total of \geq 3/23 responses (inclusive of the original 14 patients from stage I) are seen then this Cohort will be deemed worthy of further investigation. This assumes an unacceptable response rate of 3% and a desirable response rate of 20% with a Type I error rate of 5% and a Type II error rate of 15%.

For Cohort 2 if \geq 2/16 complete or partial responses are seen by RECIST 1.1 criteria within 6 months of treatment (stage I) then the study will expand to stage II. If a total of \geq 5/25 responses (inclusive of the original 16 patients from stage I) are seen then this Cohort will be deemed worthy of further investigation. This assumes an unacceptable response rate of 10% and a desirable response rate of 30% with a Type I error rate of 10% and a Type II error rate of 10%.

For Cohort 3 if \geq 4/19 complete or partial responses are seen by RECIST 1.1 criteria within 6 months of treatment (stage I) then the study will expand to stage II. If a total of \geq 11/36 responses (inclusive of the original 19 patients from stage I) are seen then this Cohort will be deemed worthy of further investigation. This assumes an unacceptable response rate of 20% and a desirable response rate of 40% with a Type I error rate of 10% and a Type II error rate of 10%.

For Cohort 4 if \geq 1/14 complete or partial responses are seen by RECIST 1.1 criteria within 6 months of treatment (stage I), then the study will expand to stage II. If a total of \geq 3/23 responses (inclusive of the original 14 patients from stage I) are seen then this Cohort will be deemed worthy of further investigation. This assumes an unacceptable response rate of 3% and a desirable response rate of 20% with a Type I error rate of 5% and a Type II error rate of 15%.

Secondary/Exploratory objectives:

To evaluate the safety and tolerability of onapristone ER alone or in combination with anastrozole in these patient populations toxicity data will be collected at each visit and tabulated with grading by CTCAE Version 5 criteria. Dose holding and modifications will occur as described in section 9.2

The objective response rate and progression free survival (PFS) will be analyzed separately for each disease type (basket/cohort 1,2,3 and4). PFS will be defined from the start of treatment to disease progression or death (whichever occurs first) or last follow-up. Kaplan Meier estimates will be used to estimate the median PFS and 2-year rate. Response will be determined by RECIST 1.1 criteria. Objective response is defined as complete or partial response by week 36 or best overall response. Duration of response will be reported for the subset of patients who experience an objective response. Clinical Benefit Rate (CBR) is defined as the percentage of patients who have achieved a complete response, partial response, or stable disease lasting ≥ 16 weeks.

Patients coming off study prior to first post-baseline assessment for reasons other than toxicity or progression may be replaced following discussion with study PI, if deemed appropriate. Patients who have measurable disease present at baseline, have received at least one cycle of therapy, and have had their disease re-evaluated will be considered evaluable for response Accrual in each cohort will continue until the required number of evaluable patients in each cohort are accrued. Responses will be confirmed by repeat imaging performed at least 4 weeks after confirmed response. Binomial proportions will be assumed when calculating the 2 sided 80% confidence interval around the objective response rate for each cohort separately.

To correlate the level of PR positivity (measured by immunohistochemsirty as a continuous variable), the level of phosphorylated PR (as a continuous variable) and the level of PR target gene expression (as a continuous variable) with response to therapy (defined as complete or partial response by week 36) with onapristone ER, a non-parametric test, such as the Wilcoxon test, will be used to test whether the PR levels (continuous variable) are different in the 2 groups of responders (complete or partial response) vs non responders. Each cohort/basket will be analyzed separately.

Sample Size:

Cohort 1 has enrolled 14 patients and stopped at Stage 1. Cohorts 2 (5 patinets enrolled) and 3 (1 patient enrolled) closed early due to poor accrual. Cohort 4 will enroll 14-23 patients. This study is expected to enroll between 34 and 43patients. Accrual of 1-2 patients per month is anticipated. The study is expected to complete accrual within 12-24 months.

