Cohort 4	Onapristone ER + Anastrozole	PR+ Granulosa cell tumor	Enroll 14 patients, if ≥ 1 response(s) expand to Stage II	Expand to a total of 23 patients	≥ 3/23

All enrolled patients will be treated at the recommended phase II dose (RP2D) of onapristone ER alone (cohort 1-3) or in combination with anastrozole (cohort 4) and continue on treatment until progression of disease, intolerable toxicity, or patient refusal. This study is expected to enroll between 34 and 43 patients, enrolling 1-2 patients per month. The study is expected to complete accrual within 12-24 months.

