2.0 OBJECTIVES AND SCIENTIFIC AIMS

The following objectives will apply to each of the three Cohorts (patient populations)

Primary Objective:

1) To evaluate the efficacy, in terms of response rate (CR or PR) of onapristone ER as a single agent or in combination with anastrozole, as determined by RECIST 1.1 response within 36 weeks of treatment, in patients with PR+ recurrent or advanced granulosa cell tumor, low grade serous ovarian cancer, or endometrioid endometrial cancer.

Secondary Objectives:

- 1) To evaluate the safety and tolerability of onapristone ER alone or in combination with anastrozole in this patient population.
- 2) To evaluate the duration of response, clinical benefit rate (CR, PR, SD lasting for ≥16 weeks) and progression free survival (PFS) of patients with PR+ recurrent or advanced low grade serous ovarian cancer, granulosa cell tumor or endometrioid endometrial cancer treated with onapristone ER alone or in combination with anastrozole.

Exploratory:

- 3) To correlate the level of PR positivity (as a continuous variable) with response to therapy (defined as complete or partial response) with onapristone ER alone or in combination with anastrozole.
- 4) To correlate the level of phosphorylated PR (as a continuous variable) with response to therapy with onapristone ER alone or in combination with anastrozole.
- 5) To correlate the level of PR target gene expression (as a continuous variable) with response to therapy (defined as complete or partial response) with onapristone ER alone or in combination with anastrozole.

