9.0 TREATMENT/INTERVENTION PLAN

9.1 Treatment Plan

Enrolled patients will initiate treatment with onapristone ER 50 mg by mouth twice daily, about 12 hours apart, and anastrozole 1mg po QD in AM (if in cohort 4) beginning Day 1 of Cycle 1. A Cycle is 28 days. Onapristine ER tablets should be swallowed whole with a glass of water and food I. Onapristone ER and anastrozole should be taken at the same times each day. Missed doses will not be made-up. Vomited doses should not be retaken. All doses and missed doses will be recorded in the patient's pill diary. Patients will remain on treatment with onapristone ER 50 mg PO BID alone (cohorts 1-3) or with anastrozole 1 mg po QD (cohort 4) (with dosage adjustments as described below) until POD, unacceptable toxicity or withdrawal of consent.

While on study, patients will return for assessments with a treating physician every 2 weeks during the first cycle, and then every 4 weeks. Vital signs, toxicity assessment and blood work will be performed at each start of cycle visit. The pill diary will be collected, and a new drug supply and pill diary will be provided. A +/- 4 day window is allowed for each start of cycle assessment.

Within 30 days of starting treatment, every 8 weeks from Cycle 1 Day 1 while on treatment, and at end of study, patients will have a CT of chest, abdomen and pelvis performed, or MRI of abdomen and pelvis with CT of chest. Best overall response should be confirmed with repeat imaging performed at \geq 4 weeks. There is a +/- 7 day window for completion of interval tumor assessments by imaging.

An optional research non-billable tumor biopsy will be performed at end of treatment in consenting patients with accessible disease.

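### Cohort 4's stage I gate counts responses to 6 months while the primary endpoint counts them to 36 weeks, so a response first seen at week 32 counts for the endpoint but cannot open stage II

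*Combined protocol and SAP*

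**What the plan says.** Section 14.0 calls the design a Simon two-stage plan: "Sample size calculations are based on the Simon two-stage minimax design". For Cohort 4 the table in Section 1.0 reads "Enroll 14 patients, if ≥ 1 response(s) expand to Stage II" and then "Expand to a total of 23 patients", with success at 3 or more responses. That table, repeated in Section 4.2, puts no time limit on the gate. The text of Section 14.0 does, in wording common to all four cohorts: "complete or partial responses are seen by RECIST 1.1 criteria within 6 months of treatment (stage I) then the study will expand". It pairs the Cohort 4 rule with response rates of 3% and 20%, type I error 5% and type II error 15%.

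The primary objective in Section 2.0 uses a longer window: "as determined by RECIST 1.1 response within 36 weeks of treatment". Later in Section 14.0, objective response means CR or PR by week 36 or, alternatively, best overall response, which has no end date.

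On imaging, Section 9.1 says "Within 30 days of starting treatment, every 8 weeks from Cycle 1 Day 1 while on treatment, and at end of study", with a window of 7 days either side for interval scans. On confirmation, Section 14.0 says "Responses will be confirmed by repeat imaging performed at least 4 weeks after confirmed response". Nothing reconciles 6 months with 36 weeks, says whether the gate needs a confirmed response, or describes the shorter gate as deliberate.

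**The concern.** A two-stage design has its stated error rates only if a response means the same thing at the gate and in the final count. Here the windows differ, and the gate turns on a single event: 0 of 14 stops the cohort and 1 of 14 continues it. One stage I patient whose response appears after 6 months but before week 36 is enough to separate the two rules. Cohort 4 is the only cohort still to enrol, and Cohort 1, under the same rule, has already stopped at stage I, so the rule is one that gets used.

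**Working it through.** **Reproducing the plan.** The inputs from Section 14.0 are n1 = 14 (stop at 0), N = 23 (success at 3 or more), and rates of 3% and 20%. A minimax search at type I error 5% and type II error 15% returns exactly this design. Its exact type I error is 2.9% and its power 85.5%. It stops at stage I with probability 0.97^14 = 65.3% at a true 3%, and 0.80^14 = 4.4% at a true 20%. The sample size is correct for a single response definition.

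**Calendar.** Scans fall at weeks 8, 16, 24 and 32. Six months is about day 183 (week 26).

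- Week 32 is day 224, or day 217 at the earliest. Both fall after day 183 and before day 252 (week 36). A response first seen there is outside the gate whether or not the gate requires confirmation. Confirmation 28 days after day 224 falls on day 252.
- Week 24 is day 168, or day 161 at the earliest. The scan is inside the gate. The earliest confirmation is 161 + 28 = day 189, which is outside it. This matters only if confirmation must also fall within 6 months.

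**Reading A: 3% and 20% are 36-week rates.** Let p be the 36-week rate and L the share of responses too late for the gate. L is an assumption. The gate rate is g = p(1 − L).

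- P(stop) = (1 − g)^14.
- P(success) = P(Bin(23, p) ≥ 3) − P(no gate response in stage I and at least 3 responses in 23).
- The second term is (1 − g)^14 × Σ Bin(x; 14, q) × P(Bin(9, p) ≥ 3 − x), with q = (p − g)/(1 − g).

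At p = 0.20 the first term is 0.8668.

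| Late share L | g | P(stop) | Stop although a stage I patient responds by week 36 | Power |
|---|---|---|---|---|
| 0 | 0.20 | 4.4% | 0 | 0.8668 − 0.0115 = 85.5% |
| 5% | 0.19 | 5.2% | 0.8% | 0.8668 − 0.0164 = 85.0% |
| 10% | 0.18 | 6.2% | 1.8% | 0.8668 − 0.0226 = 84.4% |
| 25% | 0.15 | 10.3% | 5.9% | 0.8668 − 0.0514 = 81.5% |
| 50% | 0.10 | 22.9% | 18.5% | 0.8668 − 0.1543 = 71.2% |

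The fourth column is P(stop) − 0.80^14. Type I error only falls on this reading, from 2.9% to 2.1% at L = 50%.

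**Reading B: 3% and 20% are 6-month rates, and later responses are added to the final count.** Now g = p and the 36-week rate is p/(1 − L). P(stop) at 20% stays 4.4%.

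| Late share L | 36-week rates | Power | Type I error |
|---|---|---|---|
| 0 | 3.0%, 20.0% | 85.5% | 2.9% |
| 10% | 3.3%, 22.2% | 89.4% | 3.7% |
| 25% | 4.0%, 26.7% | 93.4% | 5.4% |
| 50% | 6.0%, 40.0% | 95.6% | 11.1% |

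**Reading C: 6 months governs both counts.** The stated error rates hold, but the design then tests a different endpoint from the one in Section 2.0.

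**The case against.** The best defence is that an earlier interim window can be a legitimate choice, and that 6 months is the only window Section 14.0 names beside the 3% and 20% rates. On that footing power need not fall. This stands: the direction of the effect depends on which window the rates refer to, and the plan does not say. It does not remove the conflict with the primary objective, and no passage presents the shorter gate as intended.

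The effect may also be small. Under reading A with 5% late responses, power is still 85.0%. The largest figures need half of all responses to come late, and nothing in the documents supports that share.

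Some stronger conclusions are tempting but not supported:

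- A reader might infer that a week-24 response cannot open stage II. The gate counts responses that are seen, and does not ask for confirmation inside 6 months.
- A reader might infer that the gate uses only half the endpoint's scans. That applies in-window confirmation to the gate but not to the endpoint. Applied to both on the scheduled 8-weekly scans, it leaves two scans against three.
- A reader might infer that a stop declares the combination inactive. Section 14.0 says only when a cohort expands; the stop is implied, and Cohort 1's history shows it in use.

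**Conclusion.** The conflict is real and unreconciled. Wherever the 6-month limit applies, a response first seen at week 32 counts under the primary objective and cannot open stage II. The cohort can therefore stop at 0/14 with a stage I responder.

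The size is not fixed by the documents, because they give no time to response. For 5% to 50% late responses, reading A costs between about half a point and 14 points of power. For 10% to 50% late, reading B takes type I error from 2.9% to between 3.7% and 11.1%. A reader might infer that the stated 15% type II error is simply wrong. That follows only under reading A, and only when the late share exceeds roughly 5%. What is established is that the stated error rates assume one response definition and the text supplies more than one.

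**What to change.** In Section 14.0, use one response definition for the stage I gate and the final 3/23 count. It should be a first CR or PR scan on or before week 36, dated by that scan, with the confirming scan at least 4 weeks later allowed to fall after the cut-off. Remove the best-overall-response alternative from the primary definition; otherwise gate and endpoint could still differ. Point the tables in Sections 1.0 and 4.2 to this definition.

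Open stage II as soon as one such response is confirmed. Conclude 0/14 only when each stage I patient has responded, progressed, come off assessment, or passed the week-32 scan with any pending confirmation.

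This is a wording change and restores the stated error rates. When no response has been seen by 6 months, the futility decision waits until day 231 at the latest (224 + 7), about 48 days or 7 weeks beyond day 183, plus any pending confirmation. A response seen and confirmed early opens stage II without waiting.

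If the shorter gate is deliberate, the plan should say so, state which window the 3% and 20% refer to and whether the gate needs confirmation, and restate the error rates for that rule.
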